Comparing the Effects of Upper and Lower Body Resistance Training on Pain Sensitivity

NCT05985382

7/28/2023

STUDY PROTOCOL

This study was a crossover trial of healthy participants. Participants completed a lower body resistance exercise and an upper body resistance exercise in a counterbalanced order across two sessions. Immediately before and after each intervention, participants underwent heat pain threshold and pressure pain threshold.

During the first session, participants underwent familiarization of the heat and pressure pain threshold followed by a 5 repetition maximum test for the upper body and lower body resistance exercise.

In the second and third session, participants underwent either a lower or upper body exercise in a counterbalanced order.

Lower body exercise was a bilateral leg extension conducted at 75% of the estimated 1 repetition maximum. 3 sets of 10 repetitions were performed.

Upper body exercise was a bilateral overhead shoulder press conducted at 75% of the estimated 1 repetition maximum. 3 sets of 10 repetitions were performed.

STATISTICAL ANALYSIS

To examine the immediate changes in heat and pressure pain threshold by condition, separate repeated measures ANOVAs were conducted. Simple effects decomposition with Bonferroni correction were completed. Our a priori alpha level is <0.05.

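### The crossover ANOVAs name no session or sequence term, so a session difference in pre-to-post response would enter the error term and, with unequal orders, the estimates.

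*Combined protocol and SAP*

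**What the plan says.** The STUDY PROTOCOL section describes a two-period crossover: "In the second and third session, participants underwent either a lower or upper body exercise in a counterbalanced order". Each session yields its own change score: "Immediately before and after each intervention, participants underwent heat pain threshold and pressure pain threshold". A separate first session was used for practice: "During the first session, participants underwent familiarization of the heat and pressure pain threshold".

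The STATISTICAL ANALYSIS section has three sentences. The model is given as "To examine the immediate changes in heat and pressure pain threshold by condition, separate repeated measures ANOVAs were conducted", the follow-up as "Simple effects decomposition with Bonferroni correction were completed", and the test level as "Our a priori alpha level is <0.05". Condition is the only factor named; time is implied. No session, order or sequence term appears, and the text does not show whether one was used. It also does not say which simple effects are meant. The documents give no sample size, number per order, SD or interval between sessions.

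**The concern.** Counterbalancing protects the average: with equal orders, a session effect cancels from the mean difference between exercises. It does not take the session effect out of the residual. Only a model that includes order does that.

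The effect that matters is a difference between sessions 2 and 3 in the pre-to-post response, for example if thresholds respond less to exercise on the second exposure. A session shift that is the same before and after exercise cancels from the condition x time test and from pre-to-post effects within a condition. It would matter only for the condition main effect, or for simple effects of condition at pre or at post if those are tested.

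With equal orders, the risk is that a real difference between upper and lower body exercise is missed because the error term is larger than it need be. With unequal orders, the estimates themselves move, and whether type I error then exceeds 5% depends on the imbalance and on N.

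**Working it through.** **Inputs.** The documents supply the design (two exercises, two sessions, pre and post measurement, counterbalanced order) and alpha 0.05, taken as two-sided. They state no power or sample size, so there is no figure to reproduce. Everything else is assumed: N = 20 to 100, a true effect tau giving 80% power when there is no session effect (0.660 SD at N = 20, 0.529 at 30, 0.454 at 40, 0.368 at 60, 0.283 at 100), and a range of p.

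**Model.** Let D be a participant's lower-minus-upper difference in pre-to-post change, with within-sequence SD 1. Let p be the session 3 minus session 2 difference in pre-to-post change. Then D = tau + s·p + e, where s = +1 if lower body exercise came in session 3 (n1 participants) and -1 if it came in session 2 (n2 participants).

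**Test without the term.** In a 2x2 within-subject ANOVA the condition x time F is the squared one-sample t on D. A numerical check gave 0.001135 both ways, and F did not change when a constant of 3 was added to all values of one session. It follows that:
- the mean of D is tau + p(n1 - n2)/N;
- the expected error variance is 1 + 4·n1·n2·p²/[N(N - 1)]. At 10/10 and p = 0.5 this is 1 + 4·10·10·0.25/(20·19) = 1.26.

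**Test with the term.** The estimate is the unweighted mean of the two sequence means, with SE = sqrt[(1/n1 + 1/n2)/4] and N - 2 degrees of freedom. It does not depend on p.

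**Equal orders, N = 20 to 100:**

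| p (SD) | Power without term | Type I error without term | Power with term |
|---|---|---|---|
| 0.1 | 79.7% | 4.9% | 80% |
| 0.25 | 78% | 4.3-4.4% | 80% |
| 0.5 | 72-73% | 2.9% | 80% |
| 0.75 | 62-64% | 1.4-1.5% | 80% |

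**Orders 11/9, N = 20.** The shift is p·2/20.

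| p (SD) | Shift (SD) | Power, shift opposes effect | Power, shift adds to effect | Type I error | Power with term |
|---|---|---|---|---|---|
| 0.25 | 0.025 | 75% | 81% | 4.5% | 79% |
| 0.5 | 0.05 | 65% | 79% | 3.3% | 79% |
| 0.75 | 0.075 | about 50% | 74% | 2.0% | 79% |

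**Orders split 60/40.** The shift is 0.2p: 0.05, 0.10 and 0.15 SD. At p = 0.5, type I error without the term is 4.5% (N = 20), 5.3% (30), 6.2% (40), 7.9% (60) and 11.7% (100), against 5.0% with it. At 12/8 it stays below 5% for all three p (4.9, 4.5 and 3.8%).

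**Pre-to-post effect within one exercise.** The shift is half as large, (p/2)(n1 - n2)/N, with opposite signs for lower and upper. At 10/10, p = 0.5, alpha 0.025 and a between-session correlation of changes of 0 to 0.5, power is 76-78% without the term and 79.6% with it.

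**Carryover.** Suppose lower body exercise carries 0.4 SD into session 3 and upper carries none. The adjusted estimate is biased by -0.4/2 = -0.20 SD at any split. The unadjusted bias is p(n1 - n2)/N - 0.4·n2/N. At p = 0.5 this is -0.20 at 10/10, 0.10 - 0.16 = -0.06 at 12/8, and -0.10 - 0.24 = -0.34 at 8/12.

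**The case against.** The strongest reply is that silence is not exclusion. Three sentences cannot show that order was left out, and the design already guards against session effects by counterbalancing, a familiarization session and a fresh pre-exercise measurement each time. With equal orders the test is conservative, and the loss is 0.3 power points at p = 0.1 and about 2 at p = 0.25. The larger losses need a p for which the documents give no evidence. The inflated type I errors need a 60/40 split in a larger trial, which sits badly with counterbalancing unless dropout was lopsided; at 11/9 and 12/8 with N = 20 there is no inflation.

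Much of this stands. It limits the size of the problem and makes lost power, not a false positive, the realistic harm. It does not remove the point: followed as written, the plan leaves an avoidable source of variation in the error term, and naming order in the model is a better analysis as well as a clearer report.

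Two further objections concern the remedy. First, under differential carryover the adjusted estimate can be more biased than the unadjusted one, as at 12/8 above. That is a chance cancellation of two biases, which reverses at 8/12; still, carryover is not cured, and the interval between sessions is not given. Second, a sensitivity analysis beside the planned ANOVA does not restore power to the planned test. That is correct, and it is why the adjusted model is better as the main analysis.

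**Conclusion.** The concern holds. No session or sequence term is specified for a design that needs one to benefit fully from its balance. With equal orders there is no bias, and the cost is power: negligible at p = 0.1 SD, about 2 points at 0.25, 7-8 at 0.5 and 16-18 at 0.75. With unequal orders the condition x time estimate also shifts by p(n1 - n2)/N, and the within-exercise effects by half that, in opposite directions. Type I error rises above 5% only for some combinations of imbalance and N.

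These sizes assume normal errors, 80% nominal power and the stated values of p and N; none of them is evidence about this trial. If the pre-to-post response did not differ between sessions, the planned analysis loses nothing. The change is one the sponsor should make. Confidence is medium, because the true session effect and the numbers per order are unknown.

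**What to change.** For each threshold, regress each participant's lower-minus-upper difference in pre-to-post change on sequence coded +1/-1, and report the intercept as the condition x time effect. Equivalently, add sequence and its interactions to the ANOVA and use the unweighted mean of the two sequence means. Treat all simple effects the same way: for pre-to-post within an exercise, regress that exercise's change on sequence and report the intercept. Keep the Bonferroni correction and list the simple effects tested.

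Report the number analysed per sequence and the interval between sessions. State that the adjustment removes session effects but not differential carryover.

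The analyses are described in the past tense. If the planned ANOVA remains the main result, give the adjusted model beside it as a sensitivity analysis, labelled as added later, and say which result governs.

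No new data are needed. The cost is one error degree of freedom and a little precision if orders are unequal. At N = 20 with no session effect, power is 79.8% (10/10), 79.4% (11/9), 78.1% (12/8) or 76.0% (13/7), against 80.0% without the term.

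### The planned ANOVA names no sequence term for a counterbalanced crossover; adding one is a low-cost gain in precision and robustness, not the repair of an error

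*Combined protocol and SAP*

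**What the plan says.** The Study Protocol section describes the design: "This study was a crossover trial of healthy participants", and "Participants completed a lower body resistance exercise and an upper body resistance exercise in a counterbalanced order across two sessions". Both thresholds are measured on either side of each exercise bout: "Immediately before and after each intervention, participants underwent heat pain threshold and pressure pain threshold". An introductory visit precedes the two exercise visits: "During the first session, participants underwent familiarization of the heat and pressure pain threshold".

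The Statistical Analysis section gives the between-condition analysis as "To examine the immediate changes in heat and pressure pain threshold by condition, separate repeated measures ANOVAs were conducted", followed by "Simple effects decomposition with Bonferroni correction were completed" and the significance level: "Our a priori alpha level is <0.05".

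The factors of the ANOVA are not listed, and no sequence, order, period or covariate term is named. The documents also give no sample size, numbers per sequence, standard deviations, correlations, or interval between the two exercise sessions.

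**The concern.** Counterbalancing deals with a session-to-session trend at the design stage: with equal numbers in each order, the trend cancels out of the mean difference between conditions. It does not cancel out of the error. If thresholds respond differently in the third session than in the second, through practice, adaptation or anything else tied to time, participants who did the lower body exercise first and those who did it second are shifted in opposite directions. An analysis that ignores order counts this spread as noise.

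What is at stake is mainly power. If the two orders end up with unequal numbers, for example after dropout, the trend no longer cancels and the estimate itself is biased.

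**Working it through.** **Inputs.** From the documents: two conditions, two exercise sessions, pre and post values in each, and alpha 0.05 (sidedness not stated; a one-degree-of-freedom F test is two-sided). Assumed, because not given: N of 10, 16, 24 or 40, period effects of 0, 0.25 or 0.5 SD, and an effect size giving 70% power when there is no trend. The plan has no figure to reproduce.

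**Step 1: what the test is.** For each participant let D = (post − pre, lower) − (post − pre, upper). The condition-by-time F of a two-by-two repeated measures ANOVA is the squared one-sample t on D. In a test data set of 20 participants both were 1.8129. An ANOVA run directly on change scores gives the same test. So both natural readings lead to D, tested on N − 1 degrees of freedom.

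**Step 2: model with a trend.** D = δ + p·s + e. Here s is +1 or −1 for the two orders, p is the between-session difference in mean change, and e has SD 1, so p is in SDs of D.

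**Step 3: equal sequences, large-sample arithmetic.** The mean of D is unbiased with true variance 1/N, but without a sequence term the error variance is estimated as 1 + p².
- p = 0.5: √1.25 = 1.118, so the effective critical value is 1.96 × 1.118 = 2.191. Type I error = 2 × (1 − Φ(2.191)) = 2.8%. For 70% power the standardized effect is 1.960 + 0.524 = 2.484, so power = Φ(2.484 − 2.191) = Φ(0.293) = 61.5%.
- p = 0.25: √1.0625 = 1.031, critical value 2.020, type I error 4.3%, power = Φ(0.464) = 67.9%.

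**Step 4: equal sequences, exact.** Without the term, (N − 1)S² is noncentral chi-square with N − 1 degrees of freedom and noncentrality N·p², independent of the mean; power follows by numerical integration. With the term, the test is an ordinary t on N − 2 degrees of freedom whatever p is.

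| N | No term, p = 0 | No term, p = 0.25 | No term, p = 0.5 | With term, any p | Type I error, no term, p = 0.5 |
|---|---|---|---|---|---|
| 10 | 70% | 67.5% | 60.4% | 68.7% | 3.0% |
| 16 | 70% | 67.7% | 60.8% | 69.6% | 2.9% |
| 24 | 70% | 67.7% | 61.1% | 69.8% | 2.9% |
| 40 | 70% | 67.8% | 61.2% | 69.9% | 2.9% |

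The term gains 8 to 9 points at 0.5 SD and about 1 to 2 points at 0.25 SD. With no trend it costs about 1.4 points at N = 10 and under 0.5 point from N = 16. Its type I error is 5%.

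**Step 5: unequal sequences.** The bias without the term is p × (n1 − n2)/N. At 15:9 with p = 0.5 it is 0.5 × 6/24 = 0.125 SD. Simulated type I error is 5.9% without the term and about 5.0% with it. Imbalance does not always inflate the error rate: at 12:8 with a 1 SD period effect the bias is 1 × 4/20 = 0.20 SD in size, but the inflated error keeps rejection at about 3.0%. Removing the bias has a price: at 15:9 the adjusted variance is ¼(1/15 + 1/9) = 0.0444 against 1/24 = 0.0417.

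**Step 6: why not also estimate a baseline slope in the main analysis.** The change score fixes at 1 the slope on the pre-exercise lower-minus-upper difference. Let r be the correlation of the pre and post lower-minus-upper differences. With equal SDs the large-sample variance ratio, estimated slope against fixed slope, is (1 − r²)/[2(1 − r)] = (1 + r)/2, or 0.75 at r = 0.50. With post SD 1.25 times pre SD it is about 1.00 at r = 0.80, so nothing is gained. In simulation against the same 70% reference, with sequence also in the model, power is 80% at N = 24, r = 0.50 with equal SDs. It is 68% at N = 24, r = 0.80, and 63% at N = 10, r = 0.90, when post SD is 1.25 times pre SD. Differential carry-over that shifts the pre and post differences equally biases this model by (1 − slope) × shift. For a 0.3 SD shift at r = 0.33 and equal SDs, type I error is 15.6% at N = 24 and 23.8% at N = 40, while the change score stays near 5%. Such a shift needs residual effects of the two exercises that differ by 0.6 SD, since the mean shift is half their difference.

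**The case against.** The case against is substantial.

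- **No error is shown.** The stated aim concerns immediate changes by condition, and a change-score or condition-by-time ANOVA addresses exactly that. This stands. A reader might infer that the planned test is invalid or anti-conservative. With equal sequences it is neither, and nothing in the documents says that the sequences were unequal.
- **No factors are listed at all.** Silence on order may be brevity. A reader might infer that order was left out of the analysis; the text does not establish that. If order was entered as a between-participant factor crossed with condition and time, the point is already met.
- **The trend is hypothetical.** The introductory visit makes one less likely, and at 0.25 SD the gain is small. This stands as a limit on size. It does not remove the case for the term, because the price of including it when there is no trend is so low.
- **The text is in the past tense.** If results are known, the term cannot be presented as prespecified. This stands and shapes the fix.

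A further tempting reading is that the pre-exercise values should enter the main model as a covariate with an estimated slope. The documents do not support this. The gain depends on correlations and SDs that they do not give, some plausible settings lose power, and no between-session interval is stated, so differential carry-over cannot be ruled out. The planned change score cancels a shift common to pre and post; the slope model does not.

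**Conclusion.** The point holds as an optional improvement in precision and robustness. On the natural reading of the Statistical Analysis section, the ANOVA leaves any session-to-session trend in the error. The consequence is lost power when sequences are equal and, in addition, bias when they are not.

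The size depends wholly on an assumed period effect: worthwhile at 0.5 SD, slight at 0.25 SD, and nil or a small loss at zero. The figures further assume normal differences, a common variance in the two orders, and a factor structure that the documents imply but do not state. They do not depend on the pre/post correlation, except where a baseline slope is considered.

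**What to change.** State the factors of each ANOVA. Keep the change-score or condition-by-time ANOVA as the main analysis for each threshold, and add sequence as a between-participant factor crossed with condition and time. Equivalently, regress each participant's D on sequence coded +1/−1 and test the intercept. The crossing matters: a sequence main effect alone leaves the within-participant error unchanged. Report the number of participants in each order. The Bonferroni-corrected simple effects can stay.

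A model that also estimates the slope on the pre-exercise lower-minus-upper difference may be reported as a labelled sensitivity analysis only, together with the mean pre-exercise difference and its confidence interval.

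If results are already known, report the sequence-adjusted ANOVA alongside the planned one and label it as added afterwards.

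Cost: no new data and one degree of freedom. If there is no period effect, that is about 1 to 1.5 points of power at N = 10 and about 0.6 or less from N = 16. With unequal sequences there is also a modest rise in variance, as the 15:9 example shows.

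### A mixed model with period terms, fitted to all available readings, would be a cheap improvement on the planned complete-case repeated measures ANOVA; the missing-data gain is conditional and mostly small

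*Combined protocol and SAP*

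**What the plan says.** The STUDY PROTOCOL section describes the design: "This study was a crossover trial of healthy participants". Each exercise had its own visit: "In the second and third session, participants underwent either a lower or upper body exercise in a counterbalanced order". On measurement: "Immediately before and after each intervention, participants underwent heat pain threshold and pressure pain threshold". Each outcome therefore has four readings per participant, a before and an after reading in each of two conditions.

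The STATISTICAL ANALYSIS section has three sentences. The aim is stated as "To examine the immediate changes in heat and pressure pain threshold by condition", and for this "separate repeated measures ANOVAs were conducted". Next, "Simple effects decomposition with Bonferroni correction were completed". Last, "Our a priori alpha level is <0.05". The section names no period or order term and does not say whether the simple effects depend on a significant interaction. The documents give no sample size and mention no missed session or reading.

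**The concern.** Two features of the method are at issue.

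- **Complete cases.** A classical 2 x 2 repeated measures ANOVA needs all four cells for each participant. Someone who attends one exercise visit and not the other contributes a full before-after change that the ANOVA cannot use. Since the ANOVAs are separate, a gap in the heat readings affects only the heat analysis.
- **Period.** Without a period term, any difference in change between the two exercise visits (from practice with the test, for example) goes into the error term. It also shifts the exercise contrast if the two orders end up unequal in size.

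At stake are some precision, possible bias in the within-condition changes, and their false-positive rate. The comparison of the two exercises is much less exposed.

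**Working it through.** The plan has no sample size, power or dropout figure to reproduce. From the documents come the four readings per outcome, the two counterbalanced orders and alpha 0.05. Everything else is assumed: N of 20, 30 or 40; correlation r between a participant's two change scores (after minus before) of 0 to 0.7; 5% to 20% of participants missing a session; two-sided tests; and two within-condition simple effects at 0.05/2 = 0.025. Changes are in SD units.

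**1. Precision of the upper-versus-lower contrast.** Let n participants have both sessions and m have one, split evenly over conditions. Leaving period aside, the information on the difference in mean change is n/[2(1-r)] + m/4. The effective number of pairs is therefore n + m(1-r)/2, against n for complete cases, and the variance ratio is n/[n + m(1-r)/2].
- 17 pairs plus 3 single sessions, r = 0: 17/18.5 = 0.919. With r = 0.6: 17/17.6 = 0.966.
- 19 pairs plus 1, r = 0: 19/19.5 = 0.974. With r = 0.6: 19/19.2 = 0.990.
- With period terms in both analyses and 9+8 complete pairs, the exact ratios for 3 missed sessions are 0.917, 0.933, 0.949 and 0.965 at r = 0, 0.2, 0.4 and 0.6. For 1 missed session they are 0.973, 0.978, 0.984 and 0.989.

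So the variance falls by 1-3% (one missed) or 3-8% (three missed). These ratios treat the covariance as known and are best cases. When the covariance is estimated by REML, in simulation at 15% dropout that depends on first-session change, the ratio is 0.98 to 1.01.

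**2. Precision of the simple effects.** The sum of the two mean changes has effective size n + m(1+r)/2. Combining sum and difference, the variance of one condition's mean change is (1/4){2(1+r)/[n + m(1+r)/2] + 2(1-r)/[n + m(1-r)/2]}. Take N = 30 with 6 missing a session, so 24 complete cases.
- r = 0: effective size 27.0 for the simple effect and 27.0 for the contrast.
- r = 0.5: (1/4)(3/28.5 + 1/25.5) = 0.0361, effective size 27.7, against 25.5 for the contrast.
- r = 0.7: 28.4 against 24.9.

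The gain is concentrated in the simple effects only when changes correlate across sessions. Paired tests on available data already use 24 + 3 = 27 participants per condition. Against them, the SE reduction at r = 0.5 is 1 - sqrt(27/27.7), about 1%.

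**3. Bias of the simple effects.** Suppose 15% miss the second exercise visit, with the odds of leaving changing 2.7-fold per SD of first-session change. If those with small changes leave, the retained participants' mean first-session change is too high by 0.133 SD (numerical integration) and their second-session change by 0.133r. Each condition is taken first by half the participants.
- Complete cases: 0.133(1+r)/2 = 0.08, 0.09 and 0.11 SD at r = 0.2, 0.4 and 0.6.
- Available pairs: (0.85/1.85) x 0.133r = 0.01, 0.02 and 0.04 SD.
- Mixed model, by simulation: under 0.005 SD.

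The sign reverses if those with large changes leave. The complete-case bias is the same in both conditions, so it cancels from the contrast when there is no true difference. At 5% dropout, the complete-case bias is 0.03-0.04 SD.

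**4. Chance of at least one false simple effect** (simulation, same scenario, r = 0.2 to 0.6):

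| Analysis | N = 20 | N = 40 |
|---|---|---|
| Complete-case, ungated | 0.058-0.068 | 0.075-0.092 |
| Available pairs, ungated | 0.049-0.050 | 0.047-0.052 |
| Mixed model, ungated | 0.046-0.048 | 0.046-0.048 |

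If a significant interaction is required first, the complete-case figure falls to about 0.01-0.02 at both sizes. At 5% dropout, all three ungated analyses give 0.043-0.056.

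**5. Period terms.** Assume a period difference in change of 0.3 SD.
- Unequal orders: the complete-case contrast shifts by 0.3 x (9-8)/17 = 0.02 SD with 9+8 pairs and 0.3 x (10-7)/17 = 0.05 SD with 10+7. With period terms the shift is 0.
- Complete data, N = 20, equal orders: the error variance of the participant-level difference, 2(1-r), gains 0.09 x 20/19 = 0.095. That is 0.095/1.6 = 6% at r = 0.2 and 0.095/0.8 = 12% at r = 0.6.
- Cost: critical t of 2.101 (18 df) against 2.093 (19 df), a factor of 1.004.

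**The case against.** The strongest objection is that no problem is shown to exist. The account is in the past tense and says "Participants completed a lower body resistance exercise and an upper body resistance exercise in a counterbalanced order across two sessions", with both thresholds taken around each exercise. If nothing was missed, there is no missing-data gain. This stands, and it is why the missing-data part is only conditional.

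A second objection is that the stated aim, change by condition, is hardly touched. This also stands: the contrast loses little precision and, with no true difference, gains no bias.

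A third is that the simple-effect harm needs several assumptions at once: substantial dropout, dropout driven by first-session change, within-condition tests, the ANOVA's complete cases and, for the false-positive figures, no gating on the interaction. Remove one and most of the harm goes. This is correct.

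A fourth is that part of the mixed model's power advantage comes from pooling variance over conditions. For a true 0.6 SD change at N = 20 with random 15% dropout, simulated power is 0.51-0.52 for complete cases, 0.56 for available pairs and 0.59 for the mixed model. About 0.03 of the gain is pooling, which is the whole gap to available pairs, and pooling assumes equal change variances for the two exercises. That too is conceded.

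What survives is that the alternative uses at least as much data, is less exposed to selective dropout, handles period, and costs little. A reader might go further and infer that participants were lost, or that the reported pain-threshold changes are biased. The documents support neither: they give no count of missing readings and do not say which participants the simple effects use.

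**Conclusion.** The point holds as a low-priority improvement of method and not as an error. Under the 2 x 2 reading, the named ANOVA is complete-case by construction and names no period term in a counterbalanced crossover. If sessions were missed, the exercise comparison would change little (variance at most 3-8% lower with 3 of 20 missing a session). The within-condition changes could be off by about 0.1 SD, but only under the assumed dropout and a complete-case analysis of the simple effects. The claim that simple effects benefit most is true for bias; for precision it needs correlated changes. The period terms are the one part that can help with complete data, and only if a period difference exists.

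All sizes rest on assumed N, correlation, dropout rate and mechanism, and period difference. It would be wrong to infer that the upper-versus-lower result is compromised: the figures show almost no movement in that contrast.

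**What to change.** For each outcome, fit a REML mixed model to all available readings, with condition, time, condition-by-time, period and period-by-time as fixed effects and Kenward-Roger degrees of freedom. Participant, participant-by-session and participant-by-time random effects match the four-reading structure. If only whole sessions are missed, the equivalent model on change scores, with condition and period, is simpler. Take the Bonferroni-corrected simple effects from this model and keep the complete-case ANOVA as a sensitivity analysis. With complete data and no period terms, the interaction test matches the ANOVA's unless a variance estimate lies on its boundary.

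The costs are:
- slightly more analysis work, and a re-analysis if results have already been run; no new data are needed;
- one degree of freedom for period-by-time (critical t 2.101 against 2.093 at N = 20);
- possible boundary variance estimates in a small sample;
- an equal-variance assumption across the two exercises if variances are pooled.

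The protection against bias holds only if missingness depends on observed data. It would not cover, for example, absence caused by soreness that was never recorded.

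### Does the Bonferroni correction of the simple effects fail because the plan does not name the comparisons it covers?

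*Combined protocol and SAP*

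**What the plan says.** The Study Protocol section describes a two-condition crossover: "Participants completed a lower body resistance exercise and an upper body resistance exercise in a counterbalanced order across two sessions". Measurement is at two time points with two outcomes: "Immediately before and after each intervention, participants underwent heat pain threshold and pressure pain threshold".

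The Statistical Analysis section is three sentences long. The first gives the aim and the model: "To examine the immediate changes in heat and pressure pain threshold by condition, separate repeated measures ANOVAs were conducted". The second gives the follow-up: "Simple effects decomposition with Bonferroni correction were completed". The third gives the level: "Our a priori alpha level is <0.05".

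No model terms, list of simple effects, family size or rule for when follow-up tests are run appears anywhere. Neither does a sample size, a standard deviation or a power statement.

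**The concern.** Bonferroni multiplies each p-value by the number of comparisons in a family, so it is not fully defined until the family is named. If the correction is counted inside a single simple effect, there is one comparison of two means, the multiplier is 1, and the declared correction changes nothing. Counted more widely, it is 2, 4 or 8. An unadjusted p of 0.02 is significant with a multiplier of 1 or 2 and not with 4 or 8.

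The simple effects are what would support a statement that a given exercise changed a pain threshold. If the multiplier were chosen after seeing the data, or were in effect 1, such statements could be weaker than the word Bonferroni suggests.

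**Working it through.** **Inputs.** From the documents: 2 conditions, 2 time points, 2 outcomes, alpha 0.05. The condition-by-time layout is inferred, since no model terms are listed. Assumed, because the documents are silent: one measurement site per pain test, two-sided tests, sample sizes of 12 and 40, and the within-person correlations. The plan states no derived figure that could be reproduced.

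**Counting the comparisons.** Each outcome has 2 before-after effects (one per condition) and 2 condition effects (one per time point): 2 + 2 = 4. Over two outcomes there are 2 × 4 = 8. The per-comparison level is 0.05/m:

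| Family | m | Level |
|---|---|---|
| Inside one simple effect | 1 | 0.05 |
| Before-after effects, one outcome | 2 | 0.025 |
| All simple effects in one outcome, or before-after effects over both outcomes | 4 | 0.0125 |
| All simple effects, both outcomes | 8 | 0.00625 |

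**Which reading the text supports.** The aim concerns immediate changes by condition. A before-after contrast within a condition is such a change; a difference between conditions at baseline is not. The ANOVAs are separate for heat and pressure, which favours a family within each outcome. Together these point to m = 2. The text does not strictly exclude 1 or 4. It gives no positive support to a family that spans both outcomes, as m = 8 requires, and m = 1 would make the sentence announce a correction that corrects nothing.

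**Error if the correction matches the tests made.** The Bonferroni bound is the number of tests times the level: 2 × 0.025 = 0.05, or 4 × 0.0125 = 0.05. For two independent tests the exact value is 1 − (1 − 0.025)² = 0.0494.

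**Error on the least favourable reading, m = 1, one outcome, no true effects.** For two independent tests, 1 − 0.95² = 0.0975; for four, 1 − 0.95⁴ = 0.1855. Simulated paired t-tests that allow for correlation (N of 12 and 40; correlation between a person's two changes from 0 to 0.7) give:

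| Tests in one outcome | No gate | Only after interaction p < 0.05 |
|---|---|---|
| Two before-after | about 8% to 10% | about 1% to 3% |
| All four simple effects | about 16% to 17% | about 2% to 4% |

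**The gated before-after case when effects exist.** Take one outcome and m = 1.
- If neither exercise changes the threshold, the interaction is null and the gate opens at most 5% of the time.
- If the two exercises change it by different amounts, at most one of the two changes is zero, so at most one true null is tested at 0.05.
- If both change it equally and the change is not zero, neither before-after null is true.

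Error stays at or below 5% in every case, with no multiplier. This argument covers the before-after tests only. If the condition effects are tested as well, two true nulls can remain behind a real interaction, and the bound is 2 × 0.05 = 0.10.

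**How often the multiplier would change a verdict.** For a test with 80% power at 0.05, the normal approximation uses a noncentrality of 1.960 + 0.842 = 2.802. Power at m = 1, 2, 4, 8 is then 0.800, 0.712, 0.619, 0.527. Neighbouring readings differ by 0.800 − 0.712 = 0.088 and 0.712 − 0.619 = 0.093, about 9 percentage points each. The extremes, 1 against 8, differ by 0.800 − 0.527 = 0.273.

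**The case for a change.** The strongest case for a change is that a prespecified correction should fix the outcome of its own tests, and this one does not. For a real effect with 80% power at 0.05, the verdict differs between the extreme readings 27% of the time. No gate is written down, so the protection a gate gives cannot be assumed. Settling the matter needs only a sentence, and stating the multiplier already used costs no power.

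Most of this stands as description: the family and the gate are both unstated, and more test sites or all cell pairs would add further possible multipliers. Three things limit its weight.
- The 27% compares the two readings with the least support in the text; either step next to the best-supported one is worth about 9 points.
- Larger error rates arise only by pooling heat and pressure, yet testing each outcome at 0.05 is a legitimate choice and the documents claim no success on either outcome alone.
- Stating the family would record what the analyst did; it would not replace the method with a better one. The section is written in the past tense, so a multiplier may have been used and simply not reported.

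**Conclusion.** The omission is real but minor, and it does not call for a change to the plan. Bonferroni over the simple effects actually tested is a sound rule. The stated aim and the separate ANOVAs point to two before-after tests per outcome with a multiplier of 2, which holds the per-outcome error at or below 5%. The comparison the trial exists to make, upper against lower body exercise, rests on a single one-degree-of-freedom interaction test per outcome, and no choice of multiplier affects it.

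The worst per-outcome figure found is about 16% to 17%. It needs four things together: no true effects, no gate, all four simple effects tested, and a correction read as no correction. A reader of the results should look for which simple effects were tested, whether they followed a significant interaction, and the multiplier used; unadjusted p-values shown beside the adjusted ones would let any other family be applied. That is a matter for reporting.

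The conclusion rests on the inferred two-by-two layout with one site per pain test. The simulated rates also rest on assumed sample sizes and correlations; the reading of the text and the Bonferroni bounds do not.
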